4.4 Framework

This pilot trial is both a feasibility trial and an exploratory superiority trial. Feasibility outcomes will be pooled by arm and compared to pre-established targets (with the exception of feasibility outcome #5). CAC, clinical outcomes and vitamin K biomarkers will be compared between arms using an exploratory superiority framework.

4.5 Statistical Interim Analysis

No statistical interim analysis was performed.

4.6 Timing of Final Analysis

All outcomes will be analyzed after all data is collected and cleaned and after finalization of this statistical analysis plan.

4.7 Timing of Outcome Assessments

For the purpose of this Phase II study, we will evaluate study exit outcomes and process measures. We will evaluate longitudinal outcomes (every 4 months) for certain biomarkers.

5 Statistical Principles

5.1 Confidence Intervals and P-values

Feasibility outcomes will be provided descriptively as rates or proportions. To meet the feasibility target, the point estimate of the observed feasibility metric simply needs to meet or exceed the target.

Most variables will be described within arm and compared between arms using two-sided p-values stratified by site and diabetes status. We will consider a p-value <0.05 to indicate statistical significance. In this exploratory phase II study, we will not formally adjust p-values for multiplicity of tests, but will consider the potential type I and type II errors in our interpretation of results. False discovery rates may be used to help interpret nominal statistical significance of the unadjusted p-values.

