7.1 Outcome Definitions

7.1.1 Feasibility Outcomes (Primary)

The pre-specified primary outcomes are as follows:

	Outcome	Definition	Target
1	Recruitment rate	Number of participants recruited per month at each site (total eligible randomized patients per site divided by date of last randomized patient at that site minus date of first randomized patient at that site, with month defined as 30.4 days. This will exclude first phase of KGH enrollment), as well as an overall crude average of each site’s rate.	>4.17 per month
2	Compliance with study medication	Proportion of prescribed doses received (divide received doses by prescribed for each patient to get a patient level measure before summarizing).	≥90% of prescribed
3	Dropout rate	Proportion of participants who dropped out from the trial (1-[% of randomized patients who either have a known date of death during the study period OR have a non-missing CAC value measured at least 6 months after randomization]).	<20%
4	Adherence to study protocol	Proportion of participants who adhered to the study protocol (90% study medication compliance and not dropped out) (all pooled).	≥80%
5	Rates of eligible patients consented and randomized	Proportion of eligible patients who were A) consented and B) randomized to the study.	No target

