Below we provide the probability of reaching the study's feasibility targets with 80 participants. We believe that a total of 80 participants are sufficient but not excessive to ensure that it is highly probable that the study's targets will be met if and only if they should be.

1. *Recruitment of trial patients in the multi-centre iPACK-HD pilot study: Successful recruitment in the multi-centre iPACK-HD pilot trial will be defined as enrolling 50 patients in 12 months from the 4 study sites in the multi-centre pilot study (average monthly accrual ≥ 4.17). If the true accrual per month follows a Poisson distribution with a rate of 6 per month, as we expect based on recruitment rates in the iPACK-HD single-centre pilot study at Queen's University, then the chance of meeting the target will be 99.7%. On the other hand, if the true recruitment rate was an unacceptably low at 3 per month, then the chance of meeting the recruitment feasibility target will only be 1.6%.*
2. *Compliance with study medication: Successful adherence will be defined as $\geq 90\%$ of prescribed intervention being administered. For true adherence rates of 80%, 85% and 95% the chance of meeting the target will be 1%, 13% and 98% respectively.*
3. *Dropout rate: Successful rate of loss to trial completion will be defined as $\geq 80\%$ of randomized patients completing the trial. For true completion rates of 70%, 75%, 85% and 90% the probability of meeting the target will be 3%, 18%, 92%, and 99.8% respectively.*

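### The pass thresholds for dropout and recruitment differ between SAP sections 5.1 and 7.1.1 and Appendix B, so results exactly at the boundary have no single verdict and the quoted completion probabilities do not belong to the 7.1.1 rule

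*SAP*

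**What the plan says.** Section 5.1 gives one pass rule for every feasibility outcome that has a target, with no confidence interval: "the point estimate of the observed feasibility metric simply needs to meet or exceed the target".

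Section 7.1.1 sets the targets. Recruitment must be ">4.17 per month", "with month defined as 30.4 days", calculated for each site and then as a crude average of the site rates. Dropout is defined as "Proportion of participants who dropped out from the trial", with a target strictly below 20%. Compliance (at least 90%) and adherence (at least 80%) have inclusive limits.

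Appendix B reproduces the pilot protocol's definitions and the chance of meeting each target with 80 participants. Recruitment success is "enrolling 50 patients in 12 months from the 4 study sites in the multi-centre pilot study", followed by a parenthetical rate, "average monthly accrual ≥ 4.17". The dropout item begins "Successful rate of loss to trial completion will be defined as" and then gives 80% or more of randomized patients completing, which is dropout of at most 20%. Section 4.3 points to this table to justify the sample size. The SAP does not say that either boundary was deliberately changed.

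**The concern.** These are the primary outcomes, and each is decided by comparing a point estimate with a limit. At the boundary, therefore, the inequality sign is the whole decision. Exactly 20% lost passes in Appendix B, fails in 7.1.1, and passes in 5.1 if the target is taken as the number 20%, because it is then met. Exactly 50 patients in 12 months is the enrolment goal itself, yet it sits below the rounded rate printed beside it.

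Two things are at stake. One is a clear verdict at the boundary, fixed before the data are analysed, as sections 1.3 and 4.6 intend. The other is whether the pass probabilities offered in support of n=80 describe the rule that will actually be applied.

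**Working it through.** **Inputs.** n=80; true completion rates 70%, 75%, 85%, 90%; true accrual 6 and 3 per month, Poisson (all Appendix B). Limits from 7.1.1 and Appendix B. Month of 30.4 days (7.1.1).

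**1. Dropout: reproduce the stated figures.** At least 80% of 80 completing means X ≥ 64, with X ~ Binomial(80, p). Dropout strictly below 20% means at most 15 lost, so X ≥ 65.

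| True completion | Stated | P(X ≥ 64), inclusive | P(X ≥ 65), strict |
|---|---|---|---|
| 70% | 3% | 3.0% | 1.6% |
| 75% | 18% | 18.4% | 12.1% |
| 85% | 92% | 91.6% | 86.2% |
| 90% | 99.8% | 99.8% | 99.5% |

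The stated figures are those of the inclusive rule. Moving to the strict rule costs 18.4 − 12.1 = 6.3 points at 75% and 91.6 − 86.2 = 5.4 points at 85%. Each difference is the probability of exactly 64 completers. If true completion were 80%, that probability would be 56.6 − 45.5 = 11.1%.

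**2. Dropout: dependence on n.** The two rules can disagree only if exactly one fifth are lost, which requires n divisible by 5. At n=79, 20% is 15.8 patients, so both rules allow at most 15 lost and need 64 completers. Both then give 1.9%, 13.3%, 87.3% and 99.5% at the four completion rates.

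**3. Recruitment: the rate.** 50/12 = 4.1667, which is below 4.17. In 30.4-day months, 50 over 365 days is 50 × 30.4/365 = 4.164 (short of 4.17), while 50 over 364 days is 50 × 30.4/364 = 4.176 (above it). The shortfall comes from rounding, and changing > to ≥ does not remove it.

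**4. Recruitment: reproduce the stated figures.** The 12-month count is Poisson with mean 12 × 6 = 72 or 12 × 3 = 36. To exceed 4.17 per month over 12 months takes 51 patients (51/12 = 4.25).

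| True rate per month | Stated | P(X ≥ 50) | P(X ≥ 51) |
|---|---|---|---|
| 6 | 99.7% | 99.7% | 99.6% |
| 3 | 1.6% | 1.6% | 1.1% |

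These figures are for the pooled count over 12 months. They are not the operating characteristics of the 7.1.1 metric, which averages site-specific rates, each over that site's own interval from first to last randomization.

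**The case against.** **Reversed direction.** A reader might infer from 5.1 that high dropout counts as success. Taken literally at n=80, a rule of 16 or more lost would pass 98.4% of the time at 30% true dropout and 0.5% at 10%. The document does not support that reading: 7.1.1 prints the dropout target with its own less-than sign, so the intended direction is plain and nobody is likely to score it backwards. What remains is loose wording, and an open question about a result of exactly 20%.

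**Knife edge.** The dropout rules differ only when n is a multiple of 5. Section 5.2 excludes one randomized patient. If 80 were randomized (an assumption, since the SAP gives no final count) and that patient leaves the denominator, n is 79 and the conflict disappears. This stands as a limit on the practical effect. It does not reconcile the sections, and Appendix B's figures are explicitly for 80.

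**Recruitment.** A reader might infer that Appendix B passes the planned 50 and only 7.1.1 fails it. In fact Appendix B carries the same rounded rate in its own parenthetical, so the conflict lies partly within that one sentence. Nor does it follow that the trial would be scored a failure for enrolling 50 in a year, because 7.1.1 never calculates a pooled rate.

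**Status of the figures.** Appendix B is quoted planning material, enrolment was already complete when the SAP was written, and observed values will be reported for readers to judge. That lowers the stakes, but it does not give the analyst one boundary to apply.

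**Conclusion.** The inconsistency is real and minor. For dropout, 7.1.1 is strict and Appendix B is inclusive, while 5.1 lets a metric pass by merely meeting its target. With 80 patients, 16 lost has no single verdict, and the quoted completion probabilities overstate those of the 7.1.1 rule by up to about 6 percentage points. This rests on a denominator of exactly 80; the two rules are the same at any n not divisible by 5. For recruitment, the rounded 4.17 puts the planned 50 in 12 months just below the limit in both places. The effect on the pass probabilities is at most half a percentage point, and it applies to the pooled count only. Nothing here changes a result away from the boundary, and the documents do not support a claim that dropout would be scored in reverse.

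**What to change.** - **Section 5.1:** say that the point estimate must be *at or better than the target in the favourable direction*.
- **Section 7.1.1, dropout:** set the target to at most 20% (at least 80% completing), which matches Appendix B and its probabilities. Alternatively, keep strictly below 20%, make that exception explicit in 5.1, and note beside Appendix B that the n=80 probabilities under this rule are 1.6%, 12%, 86% and 99.5%.
- **Recruitment, in 7.1.1 and as a note to Appendix B:** express the target as at least 50/12 per month in total across sites, unrounded. Say that it is compared with a total rate: 50/12 is a four-site total, about 4.167/4 = 1.04 per site, so an average of site rates is not on the same scale.

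The cost is SAP wording only, with no new data or analyses. The boundaries should be settled before the feasibility results are seen.

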5.2 Analysis Populations

All analyses will use a modified intent-to-treat population using all available data. However, one patient who developed an exclusion criteria post-randomization but did not receive any study intervention will be excluded from primary analysis. Thus, all randomized patients will be analyzed in the arm they were randomized to regardless of treatment compliance or data completion.

6 Trial Population

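### Section 5.2 excludes one randomized patient and then says all randomized patients are analysed; read literally, the exclusion also conflicts with the dropout denominator in 7.1.1

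*SAP*

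**What the plan says.** Section 5.2 makes three statements in sequence. It opens with "All analyses will use a modified intent-to-treat population using all available data". It then says that one patient, who developed an exclusion criterion after randomization and "did not receive any study intervention will be excluded from primary analysis". It ends with "Thus, all randomized patients will be analyzed in the arm they were randomized to regardless of treatment compliance or data completion".

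Section 7.1.1 designates the five feasibility outcomes as the primary outcomes. Their populations are described differently:

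- Outcome 1 (recruitment) counts "total eligible randomized patients per site divided by date of last randomized patient at that site".
- Outcome 2 (compliance) is "Proportion of prescribed doses received (divide received doses by prescribed for each patient to get a patient level measure before summarizing", with no population named.
- Outcome 3 (dropout, target below 20%) is "1-[% of randomized patients who either have a known date of death during the study period OR have a non-missing CAC value", where the CAC value must come from at least 6 months after randomization.
- Outcome 4 (adherence, target at least 80%) requires 90% compliance and not having dropped out. Its denominator is participants.
- Outcome 5B is the proportion of eligible patients who were randomized. It has no target.

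Appendix B states the dropout criterion as at least 80% of randomized patients completing. Section 5.1 judges each target on the point estimate alone. Section 6.3 promises a flow diagram that gives the reasons for excluding randomized patients.

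**The concern.** The last sentence of 5.2 is worded as a consequence of the one before it, yet contradicts it. Section 1.3 says that the SAP is there to fix exactly what will be analysed, but two analysts could use different denominators here and both cite 5.2.

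The denominator matters because of what is primary in this trial. In a feasibility trial, a patient lost between randomization and first dose is part of what the primary outcomes are meant to describe. An exclusion from the primary analysis, taken at its word, falls on those outcomes and overrides a dropout definition written for randomized patients. The pass/fail rule has no interval around the estimate, so one patient can decide a verdict at the boundary.

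**Working it through.** **Inputs.** Planned total 80 (section 4.3; the number actually randomized is not given). Dropout target <20% and adherence target ≥80% (7.1.1). Completion target ≥80% of randomized patients (Appendix B). Decision on the point estimate (5.1).

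**1. The plan's own figures.** With X completers ~ Binomial(80, p), P(X ≥ 64) at p = 70%, 75%, 85% and 90% is 3.0%, 18.4%, 91.6% and 99.8%. Appendix B states 3%, 18%, 92% and 99.8%, so the figures reproduce. Appendix B therefore works with all 80 and treats 64/80 completing (20.0% dropout) as a pass. The strict <20% rule needs X ≥ 65 and would give 1.6%, 12.1%, 86.2% and 99.5%.

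**2. Size of the shift in dropout.** Let d be the dropouts among the other 79, and suppose this patient is also a dropout under 7.1.1.

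- Patient excluded: d/79. Patient included: (d + 1)/80.
- Difference: (79 − d)/(79 × 80) = (79 − d)/6320.
- At d = 15: 64/6320 = 1.0 point. At d = 0: 79/6320 = 1.25 points, the maximum.

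**3. When the verdict changes, at 80 randomized.**

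| Total dropouts, with this patient | Included | Excluded | Strict <20% | ≥80% completing |
|---|---|---|---|---|
| 15 | 15/80 = 18.8% | 14/79 = 17.7% | both pass | both pass |
| 16 | 16/80 = 20.0% | 15/79 = 19.0% | included fails, excluded passes | both pass |
| 17 | 17/80 = 21.3% | 16/79 = 20.3% | both fail | both fail |

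**4. How likely that count is.** For Y dropouts ~ Binomial(79, q), P(Y = 15) is 7.2%, 10.2% and 11.4% at q = 15%, 17% and 19%; these rates are assumptions. At q = 15%, the chance of meeting <20% is P(Y ≤ 15) = 87.3% with the patient excluded and P(Y ≤ 14) = 80.1% with the patient included. The gap of 7.2 points is P(Y = 15). Under the completing rule it is 87.3% either way.

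**5. Other totals.** For 76 to 89 randomized, the strict dropout verdict changes at no more than one count, and at none for 76, 81 and 86. The ≥80% completing rule, which does not flip at 80, can flip at neighbouring totals: with 79 randomized and 16 dropouts, 63/79 = 79.7% fails and 63/78 = 80.8% passes.

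**6. Adherence and compliance.** With a adherent patients among the other 79, excluding a non-adherent patient moves adherence from a/80 to a/79, again about 1 point. At 80 randomized no verdict changes: 63/80 = 78.8% and 63/79 = 79.7% both fail; 64/80 = 80.0% and 64/79 = 81.0% both pass. For compliance, if it is summarized as a mean and this patient is entered as 0%, a mean of 90.0% in 79 becomes 79 × 90.0/80 = 88.9% in 80. The other 79 would need 90 × 80/79 = 91.1%. If no dose was prescribed, the ratio is undefined and this step does not apply.

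**The case against.** The strongest reply is that this is a wording slip in a plan that is otherwise open about the exclusion. Section 5.2 calls the population modified, states the single exclusion and its reason, and section 6.3 will show it in the flow diagram, so a reader can put the patient back. The dropout outcome also carries its own denominator, and a specific definition can be read as overriding a general statement. Much of this stands: nothing is concealed, and the patient may stay in the dropout rate after all. It does not settle the matter, because the SAP does not say which statement governs, and the flow diagram does not say which denominator decides the verdict.

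A reader might infer more than the text supports:

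- **That the patient is dropped from every analysis.** The exclusion is worded for the primary analysis. The wider scope is an inference from the opening sentence of 5.2.
- **That a failure is being removed.** The SAP does not report this patient's course. A known death in the study period or a late CAC value would count as not dropped out, and compliance cannot be computed if nothing was prescribed.
- **That all the feasibility results are flattered.** For recruitment, leaving the patient out can only lower the count. Outcome 5 has no target to pass.
- **That the dropout verdict is generally at risk.** At 80 randomized the flip needs one exact count and the strict reading of the target. It owes as much to the difference between <20% and ≥80% completing as to the exclusion.

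**Conclusion.** The point holds as a minor one. Section 5.2 contradicts itself, and its exclusion, read with the primary label in 7.1.1, conflicts with a dropout rate defined on randomized patients in both 7.1.1 and Appendix B.

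Its size is about 1 percentage point on dropout near the target, and 1.25 points at most. This rests on two assumptions: that the planned 80 were randomized, and that this patient meets the 7.1.1 definition of a dropout. The documents do not support a claim that the primary results are materially biased, or that they all move in a favourable direction.

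**What to change.** Three changes of wording in 5.2, with a cross-reference in 7.1.1:

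1. Make the last sentence apply to all other randomized patients, so that it agrees with the exclusion before it.
2. Limit the exclusion to the by-arm CAC, clinical and biomarker comparisons.
3. Keep the patient in the denominator of dropout (outcome 3) and in the randomized count (outcome 5B), classified by the 7.1.1 definition. Keep the patient in adherence (outcome 4) as non-adherent, or report adherence with and without this patient.

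Leave outcome 1 on its own definition of eligible randomized patients; forcing the patient into it could conflict with the eligibility condition.

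The cost is a few sentences and no new data. Dropout and adherence may come out about 1 point less favourable.

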6.1 Screening Data

Baseline patient characteristics of randomized patients will be compared using descriptive statistics only to help assess the representativeness of the sample. Continuous variables will be described as median [Q1 to Q3].

6.2 Eligibility Criteria

Published at <https://clinicaltrials.gov/ct2/show/NCT01528800> and Holden et al. *Canadian Journal of Kidney Health and Disease* (2015) 2:17 DOI 10.1186/s40697-015-0053-x.

6.3 Screening, Recruitment, Patient Flow/Follow-up

A CONSORT style flow diagram will present the numbers of patients screened and all reasons excluded prior to randomization. The table will also include the number randomized to each arm and the number used in the primary analysis in each arm with reasons for the exclusion of randomized patients.

6.4 Baseline Characteristics

Baseline characteristics will be described by arm and overall using descriptive statistics only. Categorical variables will be described as counts (%). Continuous variables will be described as median [Q1 to Q3].

The following baseline patient characteristics will be described:

- Age, sex, ethnicity, CKD cause, number of comorbidities (0, 1, 2, >2), Charlson Comorbidity Index, weight, height, BMI, abdominal waist circumference, smoking history, parathyroidectomy, primary HD access site, primary HD access type, time from primary HD access installed to randomization, time from start of HD to randomization
- Baseline concomitant medication use
 - Calcium-based phosphate binders: calcium, calcium acetate, and calcium carbonate
 - Non-calcium-based phosphate binders: sucralfate, sevelamer hydrochloride (HCl), and lanthanum carbonate
 - Calcitriol
 - Vitamin D: ergocalciferol and cholecalciferol
 - Calcimimetic: cinacalcet HCl
 - HMG-CoA reductase inhibitors: atorvastatin calcium, fluvastatin sodium, lovastatin, pravastatin sodium, simvastatin, ezetimibe, rosuvastatin calcium, and amlodipine besylate/atorvastatin calcium
 - Angiotensin converting enzyme (ACE) inhibitors: benazepril HCl, captopril, perindopril erbumine, quinapril HCl, ramipril, enalapril, fosinopril sodium, lisinopril, and lisinopril/hydrochlorothiazide
 - Angiotensin II receptor blockers (ARBs): losartan potassium, irbesartan, candesartan cilexetil, telmisartan, eprosartan mesylate, and valsartan
 - Anti-platelet therapy: acetylsalicylic acid, clopidogrel bisulfate, and dipyridamole
- Baseline blood measures
 - Clinical lab values:
 - Hemoglobin, albumin, Kt/V, creatinine, and fibroblast growth factor-23 (FGF-23)
 - Lipid profile: high-density lipoprotein (HDL), low-density lipoprotein (LDL), triglycerides, and total cholesterol
 - Parameters of mineral metabolism: phosphate, calcium, parathyroid hormone (PTH), and alkaline phosphatase (ALP)
 - Vitamin K status: protein induced by vitamin K absence or antagonist II (PIVKA-II), growth arrest-specific 6 (Gas6), phylloquinone/vitamin K1 (PK), vitamin K2 (MK4), osteocalcin Gla, osteocalcin Glu, osteocalcin Gla to Glu ratio, percent of osteocalcin undercarboxylated, and dephosphorylated-uncarboxylated MGP (dpucMGP)
 - Biomarkers of inflammation: c-reactive protein (CRP), interleukin 6 (IL-6), leptin, insulin, glucose, homeostasis model assessment-insulin resistance (HOMA-IR)
 - Vascular inflammation variables: myoglobin, calprotectin, neutrophil gelatinase-associated lipocalin, matrix-metalloproteinase 2, osteopontin, myeloperoxidase, serum

- amyloid A, insulin-like growth factor binding protein-4, intercellular adhesion molecule 1, vascular cell adhesion protein 1, matrix-metalloproteinase 9, and cystatin C
 - Vitamin D metabolites: 1,25-OH-D3, 25-OH-D2, percent 25D that is D2, Total 25D, 24,25(OH)2D3, 25D3:24,25D3, 24,25D3:25D3, 3epi25-OH-D3, 3epi25-OH-D3(%), 1,25(OH)2D3, 1,24,25(OH)3D3, 1,25(OH)2D3:1,24,25(OH)3D3, 1,25(OH)2D3:1,24,25(OH)3D3
- Agatston and volume calcium scores and abdominal aortic calcification (AAC) scores
- Thoracic and lumbar vertebral fractures
- Body composition:
 - Cross-sectional area (cm² or cm²/m²): muscle, normalized muscle, intermuscular adipose tissue (IMAT), visceral adipose tissue (VAT), subcutaneous adipose tissue (SAT) and total adipose tissue (TAT)
 - Radiodensity (HU): muscle, IMAT, VAT and SAT

7 Analysis

